9.3. Materials and Supplies

9.3.1. LY2157299

LY2157299 will be provided as tablets in blister packs. All materials must be stored at room temperature within temperature range specified on the material label. The material will be

labeled according to regulatory requirements of the country. Should the type of clinical trial material packaging change, it will adhere to country-specific regulations.

The tablet should remain in the blister pack until just prior to administration.

9.3.2. Sorafenib

Sorafenib will be supplied in commercially available dosage forms and provided according to the country's regulatory requirements.

9.3.3. Ramucirumab

Ramucirumab will be supplied in commercially available dosage forms and provided according to the country's regulatory requirements.

9.4. Method of Assignment to Treatment

In Part A, patients who meet all criteria for enrollment will be randomized to receive 1 of 2 doses of LY2157299 after completing the screening at Visit 0. Assignment to dose cohorts will be determined by a computer-generated random sequence using an interactive voice response system (IVRS). The randomization method used should result in approximately equal numbers of patients in each dose cohort (no more than a difference of 4 patients between the 2 dose cohorts at any planned analysis while enrollment into both cohorts occurs). To achieve between-cohort comparability for stratification factors, the randomization should ensure as much balance as possible between AFP levels (≤ 400 ng/mL and >400 ng/mL), etiology (alcohol, viral hepatitis, other), and whether sorafenib naive or not, both at interim (after 20 and 80 patients have been randomized) and final analyses, the order of priority being as listed. It is important to implement a system such that treatment of eligible patients is not delayed.

The decision to stop enrolling into Cohort 1 was made based on the results from the additional data review. The remaining patients that were to be assigned to Cohort 1 (until 70 patients have been treated) who have elevated AFP levels and who meet all criteria for enrollment will be assigned by the IVRS to receive the LY2157299 300-mg/day dose (ie, transferred to Cohort 2) after completing the screening at Visit 0.

In Part B, patients who have a AFP level <1.5 x ULN and who meet all criteria for enrollment will be assigned by the IVRS to receive the LY2157299 300-mg/day dose after completing the screening at Visit 0.

Enrollment into Part B will continue during the interim analysis of Part B.

In Part C, patients who have not received prior systemic treatment and who meet all criteria for enrollment will be assigned by the IVRS to receive either the LY2157299 80 mg BID or the LY2157299 150-mg BID dose after completing the screening at Visit 0.

In Part D, patients who meet all criteria for enrollment will be assigned by the IVRS to receive either the LY2157299 80-mg BID or the LY2157299 150-mg BID dosage after completing the screening visit.

In Part E, patients who have received at least one prior line of systemic therapy or who have not received prior treatment and are ineligible for sorafenib treatment (at the investigator's discretion) and who meet all criteria for enrollment will be assigned by the IWRS to receive LY2157299 150 mg BID dosage after completing the screening visit.

The IWRS will be used to assign LY2157299 clinical trial material (eg, blister packs) containing study drug to each patient. Site personnel will confirm that they have located the correct clinical trial material by entering a confirmation number found on the packaging into the IWRS.

9.5. Dose Adjustments

9.5.1. LY2157299

If a patient experiences any of the following events that are considered possibly related to LY2157299, LY2157299 will be omitted until the event resolves:

- ANC $<0.5 \times 10^9/L$ for longer than 7 days, or ANC $<1.0 \times 10^9/L$ with a single temperature of $>101^\circ F/38.3^\circ C$ or a sustained temperature of $>100.4^\circ F/38^\circ C$ for more than 1 hour or platelet count $<25 \times 10^9/L$
- CTCAE Grade 3 or 4 nonhematologic toxicity

Nonhematological toxicity must resolve to CTCAE Grade 0, 1, or baseline (with the exception of alopecia, fatigue, skin rash, nausea, vomiting, constipation, or diarrhea that can be controlled with treatment).

Hematologic toxicity must resolve to a level that, in the opinion of the investigator, is reasonable to allow for continuation of treatment.

If dosing is delayed for more than 2 weeks, the patient should be withdrawn from the study.

For Parts A and B, patients who do recover within the 2-week time frame may have the dose reduced to 160 mg for 300-mg dose arm and to 100 mg for 160-mg dose arm.

For Parts C and D: in case of a dose delay of LY2157299, patients can continue sorafenib or ramucirumab treatment (at investigator discretion).

For Part E, patients who do recover within the 2-week time frame may have the dose reduced to 160 mg or their schedule altered after discussion between the investigator and Lilly CRP.

No patient will have his/her dose reduced more than once. Re-escalation to the previous dose is acceptable in the absence of continuing or cardiac toxicities. If subsequent dose reduction is required after re-escalation, the patient must be maintained at the reduced dose level for all remaining cycles.

If moderate or severe heart valve toxicities are observed, the patient must immediately be discontinued from the treatment (for definitions see [Attachment 12](#), including references on the echocardiographic assessment based on the Guidelines of the American and European Societies of Cardiac Echocardiography). Exceptions to this rule must be approved by the ERBs.

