8.3. Discontinuations

8.3.1. Discontinuation of Patients

The criteria for enrollment must be followed explicitly. If a patient who does not meet enrollment criteria is inadvertently enrolled, that patient is discontinued from the study drug but can be allowed to continue in the study in order to provide the follow-up data needed for the analysis of the entire intention-to-treat (ITT) population. An exception may be granted in rare circumstances because HCC patients have a serious or life-threatening condition for which there is no effective alternative therapy and, in the opinion of the investigator, is receiving benefit from study drug. In these rare cases, the investigator must obtain documented approval from Lilly to allow the patient to continue to receive study drug.

In addition, patients will be discontinued from the study drug in the following circumstances.

- The patient has evidence of objective progressive disease (radiological assessments by RECIST v1.1 or mRECIST and/or is clinically symptomatic). The important decision in determining whether or not a patient can continue on study drug could be based on their clinical symptoms, even if the patient has progressive disease based on radiological evidence. The investigator may also take into consideration biomarker responses.
- Enrollment in any other clinical trial involving use of an investigational product or enrollment in any other type of medical research judged not to be scientifically or medically compatible with this study.

- The investigator decides that the patient should be withdrawn. If this decision is made because of an SAE or a clinically significant laboratory value related to the study drug, the study drug is to be discontinued and appropriate measures are to be taken. Lilly or its designee is to be alerted immediately.
- The patient requests that he/she be withdrawn from the study drug.
- The study drug has shown unacceptable toxicity.
- The patient becomes pregnant or fails to use adequate birth control (for women with reproductive potential).
- The patient is noncompliant with study procedures, including being noncompliant with respect to taking study drug (see Section 9 on compliance).
- The patient for any reason requires treatment with another therapeutic agent that has been demonstrated to be effective for treatment of the study indication. In this case, discontinuation from the study occurs prior to introduction of the new agent.

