9.5.2. Sorafenib

Doses will be delayed or reduced for clinically significant hematologic and other toxicities (Table JBAK.7; see Table JBAK.8 for modifications due to skin toxicity) that are related to sorafenib. In case of a dose delay of sorafenib, patient can continue LY2157299 treatment (at investigator discretion).

When dose reduction is necessary, sorafenib dosage may be reduced using the predefined dose levels:

- Dose level 1 (no reduction): 400 mg (2 x 200 mg) administered orally BID daily
- Dose level 2: 400 mg (2 x 200 mg) daily
- Dose level 3: 400 mg (2 x 200 mg) every other day
- If further dose reduction is required, the patient should be discontinued from the study.

At the discretion of the investigator, the dose may be re-escalated to the previous dose level 400 mg BID after the resolution of the AE.

Table JBAK.7. Sorafenib Dose Modifications for Hematologic and Nonhematologic Toxicities

Grade	Dose Delay	Dose Modification
Hematologic toxicities		
Grade 0-2	Treat on time	No change
Grade 3	Treat on time	Decrease 1 dose level
Grade 4	Delay ^a until ≤ Grade 2	Decrease 1 dose level
Nonhematologic toxicities (except skin toxicity) ^b		
Grade 0-2	Treat on time	No change
Grade 3	Delay ^a until ≤ Grade 2	Decrease 1 dose level ^c
Grade 4	Off protocol therapy	Off protocol therapy

Source: Llovet et al. 2008 supplementary material.

^a If no recovery after 30-day delay, treatment will be discontinued unless patient is deriving clinical benefit.

^b Also excludes nausea/vomiting that has not been premedicated, and diarrhea.

^c If >2 dose reductions are required, treatment will be discontinued.

Table JBAK.8. Suggested Sorafenib Dose Modifications for Skin Toxicity

Skin Toxicity Grade	Occurrence	Suggested Dose Modifications
Grade 1: Numbness, dysesthesia, paresthesia, tingling, painless swelling, erythema or discomfort of the hands or feet that does not disrupt the patient's normal activities	Any occurrence	Continue treatment with sorafenib and consider topical therapy for symptomatic relief
Grade 2: Painful erythema and swelling of the hands or feet and/or discomfort affecting the patient's normal activities	1st occurrence	Continue treatment with sorafenib and consider topical therapy for symptomatic relief. If no improvement within 7 days, see below

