- **Postdiscontinuation from Study Drug 30-day Follow-up Period:** The time after the patient discontinues study treatment during which follow-up data are collected. Visit 801 starts 1 day after discontinuation from study treatment and lasts 30 days (± 3 days).
 - **Applies to patients in extension period, too.** However, for patients in the extension period, the end of the 30-day follow-up period is also the end of their study participation (unless further follow-up is required for safety reasons).
- **Long-Term Follow-up Period:** All subsequent long-term follow-up visits will occur at 60-day intervals (± 7 days) (for example, Visit 802, Visit 803, etc.) until the patient meets the requirements to discontinue from the study. These are the preferred windows for follow-up visits (Visit 802 and beyond); however, if some information cannot be obtained at all or not within the specified window for Visit 802 and beyond, it will not result in a protocol violation if no cardiac toxicity requiring further cardiac monitoring was observed at V801.
 - **Not required for patients in extension period (unless required for safety follow-up)**

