10.1. Efficacy Measures

All patients will be followed for progression and OS. Patients who come off therapy due to objective progressive disease will be followed for survival every 2 months. From Amendment (b), patients may continue on study treatment even if they have objective progression if they are clinically asymptomatic (see Section 8.3). However, it is important that the cycle response records objective progressive disease in the cycle that it occurred in order to

estimate time to tumor progression, progression free survival, and response rate without bias. These patients will then be discontinued from study treatment because of overall symptomatic deterioration (including biomarker response) or other causes. Patients who come off therapy and do not have objective progressive disease should be followed every 2 months after discontinuation from study treatment until death, including 6-weekly radiologic examinations until objective progressive disease is determined (using the same radiological scans as at baseline). Patients who progress should then be followed for survival every 2 months. Every attempt should be made to gather all information every 2 months (radiological scans and survival), even if a patient starts a new anticancer therapy. Evaluation of survival can be accomplished by telephone contact if necessary. The date any new anticancer therapy starts, either during the 30-day poststudy drug discontinuation period or long-term follow-up periods, needs to be collected. This will enable a better estimate of time-to-event data to inform future decisions in this indication as it will be based on more mature data.

It is important that protocol procedures related to collection of these data, both during the active study treatment phase and follow-up period, are followed and that dates of data collection are recorded accurately.

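### Three protocol rules take the patient out of the study rather than off treatment, which contradicts the progression and survival follow-up that Section 10.1 requires for everyone

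*Protocol*

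**What the plan says.** Three protocol rules take a patient out of the study:

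- Section 9.5.1, after a long LY2157299 delay: "If dosing is delayed for more than 2 weeks, the patient should be withdrawn from the study."
- Section 9.5.2, below the lowest listed sorafenib level (Part C only): "If further dose reduction is required, the patient should be discontinued from the study."
- Section 8.3.1, when another agent shown to be effective in the indication is needed: "discontinuation from the study occurs prior to introduction of the new agent."

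The study-period definitions that open Section 10 run the long-term visits "until the patient meets the requirements to discontinue from the study". SAP Attachment 3 lists two related violations. One is a patient who meets the 8.3.1 criteria and is not removed from the study. The other is a patient whose treatment is held a long time for toxicity and who stays in the study.

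Other passages point the opposite way. Section 10.1 says: "All patients will be followed for progression and OS." Section 10.1 and the synopsis ask for scans and survival every 2 months even once another anticancer therapy has begun. The synopsis follows all patients to death, and Section 7.1 follows all for OS to study completion. The 8.3.1 list that holds the new-agent bullet opens with "patients will be discontinued from the study drug in the following circumstances". Footnote c of Table JBAK.7 stops treatment, not participation, when more than two sorafenib reductions are needed.

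**The concern.** A site cannot follow both sets of instructions. If it applies the withdrawal wording, it stops scans and survival contact for patients who left because of toxicity or because they needed another therapy. Those reasons are plausibly related to later progression and death, so the censoring they create is not safely ignorable in a Kaplan-Meier estimate. TTP is the primary clinical endpoint and OS a main secondary one. The SAP's handling of missing time-to-event data (Section 5.3.4) is censoring and nothing else, so the analysis would not correct for it.

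**Working it through.** **1. Are leaving drug and leaving the study different things here?** Yes. Section 8.3.1 says an ineligible patient "is discontinued from the study drug but can be allowed to continue in the study" so that follow-up data can be collected. Section 7.1.1 records the reason for stopping treatment and the reason for leaving the study separately, and SAP 5.3.5 reports both. Section 9.5.1 itself uses treatment, not study, for heart-valve toxicity.

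**2. Does leaving the study end follow-up?** Yes, by the Section 10 definition of the long-term period. Section 7.1.1 likewise equates the end of long-term follow-up with the end of the study for the patient.

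**3. One patient, two instructions.** Take a patient without progression whose LY2157299 delay passes 2 weeks.

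- Under 9.5.1 the patient leaves the study.
- Under 10.1 the patient has 6-weekly scans until progression and survival contact until death.
- SAP Attachment 3 pulls both ways. It penalises keeping patients who meet the 8.3.1 criteria, and it also lists missed tumor scans after LY2157299 discontinuation as a violation.
- The toxicity-hold item in Attachment 3 reads 24 weeks in the text supplied, against 2 weeks in 9.5.1. This may be a reading loss in the PDF. The two must be reconciled.

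**4. Effect on the endpoints.** SAP 5.1.1 censors TTP at the last tumor assessment and OS at the last prior contact. If progression is already recorded, only OS is exposed. If not, both are.

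**5. Size: events.** The only stated figure that relies on complete follow-up is in Section 12.1: 140 patients, 24-month accrual, 6 further months, no loss, about 129 events. With exponential TTP, medians of 3 and 4.5 months (HR 1.5), λ = ln 2 / median, A = 24 and F = 6:

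P(event) = 1 − [exp(−λF) − exp(−λ(A+F))] / (λA)

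- Median 3: 1 − (0.2500 − 0.0010)/5.545 = 0.955
- Median 4.5: 1 − (0.3969 − 0.0098)/3.697 = 0.895
- Events: 70 × (0.955 + 0.895) = 129.5, which reproduces the stated figure
- Power at 129 events, two-sided 20%: Φ(√129/2 × ln 1.5 − 1.2816) = Φ(1.021) = 84.6%, against a stated approximate 80%

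The share lost before progression is not given, so a range is assumed. A constant exit hazard η, equal in both arms, is added to λ; P(event) is multiplied by λ/(λ+η); and η is set to give each share.

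| Assumed share lost | Events | Power |
|---|---|---|
| 5% | 124 | 83.5% |
| 7.4% | 121 | 82.8% |
| 10% | 118 | 82.1% |
| 15% | 112 | 80.6% |
| 20% | 106 | 78.9% |
| 30% | 94 | 75.2% |

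The 7.4% row is 11/149, the Part A and B patients who stopped treatment for adverse events (Section 5.1.5.2). It is not a count of patients lost. The loss of information is modest, and formal comparison was dropped from Amendment (b). The table measures lost events, not bias.

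**6. Size: bias.** For the proportion event-free at a fixed time, each patient of unknown status widens the worst-case range by 1/n. In Part D that is 1/18 = 5.6 points, and in Part E 1/23 = 4.3 points. Three such patients in Part E give 3/23 = 13 points. As a yardstick, that equals the gap between the 50% and 63% that Section 12.1 uses to separate a poor from a promising treatment. Three is an assumption for illustration.

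**7. Part C trigger.** Section 7.1 starts the final analysis at 85% of survival events in the expanded cohort. If that means 85% of patients, it cannot be reached once more than 15% leave before death.

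**The case against.** The strongest reply is that Section 10.1 was written for exactly this situation and governs. It covers patients off therapy without progression, keeps collecting after new therapy, and asks for that therapy's start date. SAP 5.1.1 continues survival contact after new therapy, SAP 5.3.6.3 lists post-discontinuation therapies, and Section 10.2.4 waives only certain cardiac assessments for patients on another treatment. Section 9.8 describes progression needing other antitumor therapy as ending study therapy. The 8.3.1 bullet sits under a study-drug heading. SAP Attachment 3 restates the heart-valve rule as removal from the study where the protocol says treatment, which suggests that the two words are used loosely.

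Most of this stands. A reader might infer that the plan deliberately ends follow-up for these patients, or that about 7% of outcome data were lost. The documents support neither. The intent to follow everyone is clear, no passage reports follow-up lost under these rules, and 11/149 counts treatment stops. The 8.3.1 bullet also covers only agents shown to be effective in the indication, a narrower class than any new anticancer therapy.

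What does not fall away is the conflict. Three operative rules say study, the Section 10 definition makes that the end of follow-up, and the SAP attaches a violation to two related situations. Clear intent in one section does not tell a site which instruction to obey.

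**Conclusion.** The concern holds as an internal contradiction with a possible consequence for TTP and OS. It is not a finding that follow-up is unplanned or has been lost. The consequence depends on sites applying the literal wording and on the reason for leaving being related to outcome; the first is unknown and the second is plausible. The direction of bias is also unknown. Patients leaving for toxicity may do worse than those who stay, and patients leaving for an effective agent may do better.

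The remaining reach is limited. At Amendment (e), Parts A and B were complete and Part C enrollment had closed. A change now mainly protects Part C survival follow-up and Parts D and E, about 18 + 23 = 41 patients. Those two parts go to final analysis once the last patient has stopped treatment and completed the 30-day visit, so the gain there is follow-up of patients who stop early. In groups that small a few patients matter, and Section 7.2 intends to compare Part E with the earlier schedule. The correction is worth making because it costs almost nothing.

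**What to change.** Add one statement to Section 8.3.1, cross-referenced from 9.5.1 and 9.5.2: meeting any of these rules does not by itself end study participation, and tumor and survival follow-up under Section 10.1 continues. Make the Section 10 definition of the long-term period consistent with this. In SAP Attachment 3, reword the two items so that retaining a patient for follow-up is not a violation, and reconcile the toxicity-hold duration with 9.5.1.

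The statement should not say which drug stops in Parts C and D, nor alter any delay or reduction threshold. Where Section 9.5.2 and Table JBAK.7 differ on what is stopped, the sponsor needs to reconcile them.

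The cost is a few sentences in the next amendment. Section 12.2.8 already plans SAP versions for Parts D and E, so the SAP change can go there. No data beyond those required by Section 10.1 are needed.

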9.5.2. Sorafenib

Doses will be delayed or reduced for clinically significant hematologic and other toxicities (Table JBAK.7; see Table JBAK.8 for modifications due to skin toxicity) that are related to sorafenib. In case of a dose delay of sorafenib, patient can continue LY2157299 treatment (at investigator discretion).

When dose reduction is necessary, sorafenib dosage may be reduced using the predefined dose levels:

- Dose level 1 (no reduction): 400 mg (2 x 200 mg) administered orally BID daily
- Dose level 2: 400 mg (2 x 200 mg) daily
- Dose level 3: 400 mg (2 x 200 mg) every other day
- If further dose reduction is required, the patient should be discontinued from the study.

At the discretion of the investigator, the dose may be re-escalated to the previous dose level 400 mg BID after the resolution of the AE.

Table JBAK.7. Sorafenib Dose Modifications for Hematologic and Nonhematologic Toxicities

Grade	Dose Delay	Dose Modification
Hematologic toxicities		
Grade 0-2	Treat on time	No change
Grade 3	Treat on time	Decrease 1 dose level
Grade 4	Delay ^a until ≤ Grade 2	Decrease 1 dose level
Nonhematologic toxicities (except skin toxicity) ^b		
Grade 0-2	Treat on time	No change
Grade 3	Delay ^a until ≤ Grade 2	Decrease 1 dose level ^c
Grade 4	Off protocol therapy	Off protocol therapy

Source: Llovet et al. 2008 supplementary material.

^a If no recovery after 30-day delay, treatment will be discontinued unless patient is deriving clinical benefit.

^b Also excludes nausea/vomiting that has not been premedicated, and diarrhea.

^c If >2 dose reductions are required, treatment will be discontinued.

Table JBAK.8. Suggested Sorafenib Dose Modifications for Skin Toxicity

Skin Toxicity Grade	Occurrence	Suggested Dose Modifications
Grade 1: Numbness, dysesthesia, paresthesia, tingling, painless swelling, erythema or discomfort of the hands or feet that does not disrupt the patient's normal activities	Any occurrence	Continue treatment with sorafenib and consider topical therapy for symptomatic relief
Grade 2: Painful erythema and swelling of the hands or feet and/or discomfort affecting the patient's normal activities	1st occurrence	Continue treatment with sorafenib and consider topical therapy for symptomatic relief. If no improvement within 7 days, see below
	No improvement within 7 days or 2nd or 3rd occurrence	Interrupt sorafenib treatment until toxicity resolves to Grade 0-1. When resuming treatment, decrease sorafenib dose by 1 dose level (400 mg daily or 400 mg every other day)
	4th occurrence	Discontinue sorafenib treatment
Grade 3: Moist desquamation, ulceration, blistering or severe pain of the hands or feet, or severe discomfort that causes the patient to be unable to work or perform activities of daily living	1st or 2nd occurrence	Interrupt sorafenib treatment until toxicity resolves to Grade 0-1. When resuming treatment, decrease sorafenib dose by 1 dose level (400 mg daily or 400 mg every other day)
	3rd occurrence	Discontinue sorafenib treatment

Source: FDA, 2011 (sorafenib prescribing information).

Suggested Management of Hypertension (adapted from Izzedine et al. 2009)

- Blood pressure should be checked regularly on sorafenib therapy. Hypertension should be managed in accordance with standard medical practice for sorafenib individualized to the patient's clinical circumstances (refer to local institutional guidance, other available guidelines, or Izzedine et al. 2009).
- For hypertension $>140/90$ and $\leq 160/100$: Continue sorafenib. Consider adding or adjusting anti-hypertensive medications.
- For persistent ($>160/100$) or symptomatic hypertension: Interrupt sorafenib. Resume when blood pressure improves to $\leq 160/100$. If persistent hypertension with optimal treatment consider decrease sorafenib by 1 dose level.
- In case of hypertension crisis (Grade 4), sorafenib should be withheld.

